# Cosmetic Outcome of PICO-7 Dressing Compared to Standard Abdominal Dressing for Repeat Cesarean Section

## ABSTRACT

**Background and Objectives:** This study was designed to compare cosmetic results in patients who have undergone repeat cesarean section through a Pfannenstiel skin incision when using a PICO-7 negative pressure wound dressing versus standard abdominal dressing postoperatively.

**Methods:** Twenty four English and Spanish speaking patients who underwent repeat Cesarean Section via Pfannenstiel skin incision from July 28, 2022 to January 4, 2023 at Eskenazi Hospital in Indianapolis, Indiana were enrolled. Patients were evaluated using the Patient and Observer Scar Assessment (POSAS) Scale at two, four and six weeks postoperatively. Healthcare providers were asked to fill out the Patient and Observer Scar Assessment Scale at the patients postpartum visit, which was between four to six weeks postoperatively.

**Results:** The median patient assessment scale and observer assessment scale (general) values were higher in the PICO group than in the standard abdominal dressing group at 2 weeks, equivalent at 4 weeks and lower at 6 weeks. There were no differences in the number of postoperative wound infections or readmissions, and there was 1 reported rash due to the adhesives in the PICO group that required it to be removed early.

**Conclusion:** Due to low recruitment and low response rate, this study as it currently stands cannot evaluate the PICO-7 dressing versus standard abdominal dressing. Because of the potential physical and psychological benefit of reducing complicated scar formation, further studies could be performed with a higher recruitment and follow up that would be able to provide information to determine if the PICO-7 versus other NPWT could be beneficial at improving patient's scar satisfaction after a repeat cesarean section.

Key Words: *Cesarean, POSAS, PICO, NPWT, cosmetic*

**Disclosure:** A portion of this study was supported financially by Smith and Nephew, the manufacturers of the PICO-7 NPWT device.

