## **Methods:**

### **Study design and participants:**

This study was a single site, randomized controlled trial at a teaching hospital in Indiana for patients undergoing a repeat cesarean delivery. Participants were randomized using 1:1 block randomization to placement of a PICO-7 dressing or a standard abdominal dressing (generally telfa, ABD gauze dressing, tegaderm +/- steristrips) at the time of cesarean. The standard abdominal dressing was removed approximately on postoperative day (POD) 1-2 and the PICO-7 dressing was removed approximately on POD 3-4 (prior to discharge) or at POD7 in the office. If the patient with a PICO dressing remained inpatient for longer than 7 postoperative days, the PICO dressing was removed prior to POD7, in accordance with device instructions. The patients were given routine postoperative incision care instructions during their inpatient stay, which includes education per OB-GYN residents, attending staff, and nursing.

Participants in both groups were sent electronic POSAS surveys at the two, four and six week postop window with primary outcome being aesthetic appearance (cosmesis) at six weeks. Observers (healthcare providers) were asked to complete a POSAS survey at the postpartum visit (~4-6 weeks postoperative) to rate scar quality. Participants were offered compensation with a \$25 Amazon gift card for participants who completed the requested follow up in the study. These were provided by Smith and Nephew.

The eligibility criteria is listed here as follows:

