### **Data Collection:**

The Patient Scar Assessment Scale (POSAS) rates 6 variables: scar-related pain, itching, color, stiffness, thickness, and irregularity. Each parameter is scored on a 1- to 10-point ordinal scale, with 1 indicating that the scar is comparable with normal skin and 10 reflecting the worst imaginable scar. The sum of the 6 individual parameters ranges from 6 (normal skin) to 60 (worst scar).

The POSAS patient survey was e-mailed to participants at the two, four, and six-week time intervals and data collected and stored via REDCap. Participants were sent each survey up to 3 times until a response was logged. If they did not respond electronically, each patient was then called up to 3 times. The POSAS observer survey was completed and collected at the time of the patient interview (routinely a postpartum visit). The observer (MD/DO/NP seeing the patient) was also asked to upload a picture of the cesarean section scar into the EMR. Baseline patient characteristics including maternal age, BMI, and number of prior cesarean sections were abstracted from the EMR.

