**Patient demographics:**

In total, 24 patients were recruited in this study. Follow-up moments were between August 2022 and March 2023. Inclusion and surgery took place between July 2023 and January of 2023. A total of 15 participants completed the primary study outcomes measures (on scar quality and patient-reported outcomes) and were included for analysis. The patient demographics are presented in Table 1. The median age of the participants was 29.8 years (range 25–34.5) in the standard dressing group and 34.6 in the PICO-7 group (range 27–42). The average prior cesarean sections were 1.4 (range 1–3) in the standard dressing group and 1.7 (range 1–3) in the PICO-7 group. Only one of the patients declared to have experienced any problematic scarring previous to surgery (e.g., hypertrophy and/or keloid). Most of the included patients were Caucasian (87.5%).

Table 1: Descriptive Statistics

Variable	Standard dressing (N = 5)	PICO (N = 10)
Age, Mean (SD)	29.8 (4.7)	34.6 (7.5)
BMI, Mean (SD)	37.2 (11.9)	34.0 (5.1)
Number of Prior C-sections, Mean (SD)	1.4 (0.9)	1.7 (1.1)

Language		
English	4 (100%)	5 (50%)
Spanish	0	5 (50%)
Missing	1	
Ethnicity		
Non-Hispanic or Latino	5 (100%)	6 (60%)
Hispanic or Latino	0	4 (40%)
Race		
Black/African American	4 (80%)	5 (50%)
White	1 (20%)	1 (10%)
Unknown/not reported	0	4 (40%)

The Patient Scar Assessment Scale (POSAS) rates 6 variables: scar-related pain, itching, color, stiffness, thickness, and irregularity. Each parameter is scored on a 1- to 10-point ordinal scale, with 1 indicating that the scar is comparable with normal skin and 10 reflecting the worst imaginable scar, as seen in Figure 4 and Figure 5. The sum of the 6 individual parameters ranges from 6 (normal skin) to 60 (worst scar).

At week 2, the average patient score was 33 in the standard dressing group versus 19 in the PICO-7 group. At week 4, the average patient score was 24.5 in the standard dressing group versus 25 in the PICO-7 group. At week 6, the average patient score was 26.5 in the standard dressing group versus 13.0 in the PICO-7 group. The observer score was measured between 4-6 weeks at the patients postpartum visit. The average observer score was 19 in the standard dressing group versus the 16 in the PICO-7 group.

Table 2: Comparison of patient POSOS scores between the groups

Variable	Standard dressing	PICO
POSAS score Week 2, Median (Q1-Q2)	33.0 (17-49) [N = 2]	19.0 (16-32) [N = 5]

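### The abstract reverses the week-2 result in Table 2 and gives the once-only observer scale a weekly pattern; the observer N, week-6 N and race figures also need correcting

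*Protocol*

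**What the plan says.** **Week 2.** The protocol abstract (Results) covers the patient scale and the observer scale in one sentence. It says the medians "values were higher in the PICO group than in the standard abdominal dressing group at 2 weeks", equivalent at 4 weeks and lower at 6. The Results text, under Patient demographics, says: "At week 2, the average patient score was 33 in the standard dressing group versus 19 in the PICO-7 group". Table 2 prints the same two values as medians.

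**Scale direction.** Data Collection scores each item 1 to 10, "with 1 indicating that the scar is comparable with normal skin and 10 reflecting the worst imaginable scar", and sums six items to a total of 6 to 60. Higher is worse.

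**Observer timing.** The abstract's Methods place the observer rating "at the patients postpartum visit, which was between four to six weeks postoperatively". Study design and participants gives the same timing, and Data Collection says "The POSAS observer survey was completed and collected at the time of the patient interview". The Results text repeats it: "The observer score was measured between 4-6 weeks at the patients postpartum visit". The observer-score Table 3 is not split by week. It shows one PICO patient on each row.

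**Other figures.** Statistical Analysis puts the number answering the 6-week survey at 15. The Results text says 15 completed the primary outcome measures. The same section gives 87.5% of included patients as Caucasian.

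**The concern.** Many readers see only the abstract. As written, it describes PICO scars as worse early and better later. Table 2 shows no such course: PICO is lower at week 2, level at week 4 and lower at week 6.

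Pairing the observer scale with the patient scale implies that clinicians saw the same pattern, although they rated each scar at most once. The Discussion goes further. It cites a lower observer score and overall opinion for PICO, and its closing paragraph places the observer result at 6 weeks. No N is given in either place, so one PICO rating reads as independent support for the patient result at the primary time point.

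The week-6 N matters because it is the denominator of the primary outcome and sets the reported retention. The race figure matters because it describes the population, and Table 1 describes a very different one.

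**Working it through.** **1. Direction at each visit (Table 2 medians, PICO minus standard)**

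| Visit | Standard | PICO | Difference | Abstract says |
|---|---|---|---|---|
| Week 2 | 33.0 (17–49), N = 2 | 19.0 (16–32), N = 5 | 19 − 33 = −14 | PICO higher |
| Week 4 | 24.5 (15–34), N = 2 | 25.0 (6–27), N = 5 | 25 − 24.5 = +0.5 | equivalent |
| Week 6 | 26.5 (16–36.5), N = 4 | 13.0 (10–16.5), N = 8 | 13 − 26.5 = −13.5 | PICO lower |

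The abstract is reproduced at weeks 4 and 6 and contradicted at week 2.

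**2. Could means give the abstract's direction?** With N = 2, the standard mean equals the median, 33. The brackets are headed Q1–Q2; I read them as lower and upper quartile.
- If the second and fourth of the five PICO scores are the quartiles, the largest possible mean is (16 + 16 + 19 + 32 + 60)/5 = 28.6.
- If each quartile is the average of two scores, the mean is (32 + 19 + 64)/5 = 23.0.

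Both are below 33, so means do not help.

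**3. How firm is the week-2 direction?** The two standard scores must be 17 and 49, since (17 + 49)/2 = 33. Linearly interpolated quartiles would need scores of 33 − 32 = 1 and 33 + 32 = 65, outside the 6–60 range. The PICO median lies between them: 17 < 19 < 49. Without the patient scoring 49, standard would be 17 and PICO would be higher. The quartile intervals also overlap.

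**4. Observer scale (observer-score Table 3)**
- Total: PICO 16 (N = 1), standard median 19.0 (11.5–39, N = 4). Difference 16 − 19 = −3, and 16 lies inside the standard interval.
- Overall opinion: PICO 2 (N = 1), standard median 7.0 (4–10, N = 2). Difference 2 − 7 = −5.
- Coverage: (4 + 1)/24 = 20.8% of enrolled patients have an observer total.

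One PICO rating cannot be higher, then equivalent, then lower.

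**5. Week-6 N.** Table 2 gives 4 + 8 = 12, or 12/24 = 50% of those enrolled. The text gives 15, or 15/24 = 62.5%. The 15 does match the denominators of Table 1 and the complications table (5 + 10), so it may count patients who answered any survey. The Discussion's 35% with no response does not settle this: 0.35 × 24 = 8.4. Eight non-responders (33.3%) would leave 16, and nine (37.5%) would leave 15.

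**6. Race.** Table 1 gives (1 + 1)/15 = 13.3% White and (4 + 5)/15 = 60% Black. Upper bounds for White:
- all 4 unknowns White: (2 + 4)/15 = 40%;
- the 9 enrolled patients outside Table 1 also White: (2 + 4 + 9)/24 = 62.5%.

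For denominators up to 24, 87.5% arises only as 7/8, 14/16 or 21/24. All need at least 7 White patients, and Table 1 allows at most 6. With at least 9 of the 24 recorded as Black, 21/24 is impossible. The other two fractions would need patients outside Table 1.

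**The case against.** The strongest reply is that little turns on this. The write-up already says nothing could be tested and that the study cannot evaluate the dressing. The Discussion calls the difference small and only potential. The observer table prints N = 1, so nothing is hidden. The primary time point is week 6, and its direction is reported correctly. All of that stands, and it keeps this a reporting fault, not an error in the conclusion.

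Some detail also deserves caution:
- The abstract gives a direction for observers at week 2, not a number. The exact statement is that no week-2 observer assessment was scheduled or tabulated. The qualifier attached to the observer scale (general) is undefined and might mean the overall-opinion row, but that row is also a single assessment with one PICO patient.
- The 12 against 15 may have an explanation. The enrolment and follow-up figure is not visible in the text reviewed, and Table 2 may count usable totals instead of returned surveys. Only Statistical Analysis ties the 15 explicitly to the 6-week survey. A request to reconcile is justified; a proven miscount is not.
- With 2 against 5 patients, no week-2 direction is informative, so a corrected abstract needs the same caution for week 2 as for the observer result.

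None of this reconciles the abstract's week-2 direction with Table 2, or the 87.5% with Table 1.

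**Conclusion.** The point holds. The week-2 direction in the abstract is opposite to both the Results text and Table 2, by 14 points on a 6–60 scale, and neither the scale direction nor the use of means explains it. The weekly pattern given for observers has no data behind it. The observer comparison rests on one PICO rating, which the prose does not disclose. The 87.5% figure cannot come from the patients in Table 1, nor from all 24 enrolled. The stated 15 six-week responders conflict with 12 scores in Table 2, and the documents do not say why.

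This rests on Table 2 being correct at week 2. The Results text agrees with it, but only the source data can confirm it. As the week-2 direction depends on one standard-dressing patient, correcting it shows no early benefit of PICO. The 6-week direction and the statement that the dressing cannot be evaluated do not change. This should be fixed, but it does not overturn the study's conclusion.

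**What to change.** 1. Check the week-2 patient scores by arm against REDCap. If Table 2 is right, the abstract should say lower with PICO at 2 weeks, similar at 4 and lower at 6. If the abstract is right, correct Table 2 and the Results text instead.
2. In either case, give N per arm at each visit (2 v 5, 2 v 5 and 4 v 8, standard v PICO, as now tabulated). State that the numbers at weeks 2 and 4 do not support a between-group comparison.
3. Remove the observer scale from the week-by-week sentence, and define or drop its qualifier. In the Results and Discussion, report it as one assessment at 4–6 weeks with its Ns: total 16 (N = 1) v 19 (N = 4), overall opinion 2 (N = 1) v 7 (N = 2). Say that this does not support a comparison, and stop placing it at 6 weeks.
4. Reconcile 15 with 12. State whether 15 means a 6-week response, a response to any survey, or returned forms without a usable total, and give the count behind the 35%.
5. Replace 87.5% with the Table 1 counts, or state its numerator and denominator.

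The cost is one source-data check and some text or table corrections. No new data or analysis is needed. The Discussion will read somewhat less favourably to PICO once the observer N is stated.

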### Secondary Outcomes

Table 3: Incisional Healing Complications

Variable	Standard dressing (N = 5)	PICO (N = 10)
Post-operative complications		
None	4 (80%) Where is the other person in the n	8 (80%)
Rash around incision due to adhesives	0	1 (10%)
Neuropathic pain	0	1 (10%)
Infection (superficial or deep)	0	0
Dehiscence	0	0

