Due to the open-label nature of the study, neither the participant nor the observer were blinded to the intervention. The impact of attribution bias or placebo effect is difficult to assess in an open-label study. Additionally, the questionnaire used consisted of multiple sub-questions that equated to an overall score, which has the potential to result in false significant outcomes based on multiple testing and the non-linear conversion table from absolute value to the 0–100 scale. Lastly, only one patient questionnaire (POSAS) was used in this study.

Moving forward, to be able to attempt to achieve a recruitment value to be able to analyze for statistical analysis, it would be prudent to attempt to include a larger population of patients. At Eskenazi Hospital in particular, two languages were not inclusive enough for adequate recruitment in this study in the short amount of time that recruitment was open. It would be extremely beneficial for recruitment to be able to include languages such as Haitian Creole in addition to Spanish and English. In the literature, other clinical studies on iNPWT on scar outcomes present a variety of scar outcome measures such as the Vancouver Scar Scale (VSS), Stony Brook Scar Evaluation Scale (SBSES), Visual Assessment Scale (VAS), Manchester Scar Scale (MSS) and the BIS (Body Image Scale) were used. It could be useful to incorporate more scales to ensure that there was not a false interpretation of scar outcomes by using only one scale.

In conclusion, this pilot randomized controlled trial was unable to provide any statistically significant data, but did show a lower overall score in the PICO-7 group vs the standard abdominal dressing group at the 6 week mark for both patients themselves and for observers. Because of the potential physical and psychological benefit of reducing complicated scar formation, further studies should be performed with a higher recruitment and follow up percentage that would be able to provide information to determine if the PICO-7 or other NPWT could be beneficial at improving patient's scar satisfaction after a repeat cesarean section.

Qualitative scar assessment

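### The abstract reports one of the two complications itemised in the PICO arm, and the Discussion/Conclusions give no result for the secondary objective.

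*Protocol*

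**What the plan says.** The Study outcomes section of the Protocol names one secondary objective: a comparison of incision healing complications between the two dressings up to 42 days after surgery. The SAP's statistical analysis text does not mention complications.

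The result is in the Secondary Outcomes section, in the table of incisional healing complications (the second of two tables labelled Table 3). The columns are "Standard dressing (N = 5") and PICO with N = 10. Under PICO the table lists one patient with "Rash around incision due to adhesives", one with "Neuropathic pain", and eight with none. Under standard dressing it lists four patients with none and zero in every named category. The cell for those four also holds an unresolved drafting query about the missing fifth patient.

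The Results paragraph of the abstract says: "There were no differences in the number of postoperative wound infections or readmissions", and that "there was 1 reported rash due to the adhesives in the PICO group that required it to be removed early". It does not mention neuropathic pain and gives no denominators.

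The abstract's Conclusion says that "this study as it currently stands cannot evaluate the PICO-7 dressing versus standard abdominal dressing", and then: "Because of the potential physical and psychological benefit of reducing complicated scar formation, further studies could be performed". The closing paragraph of Discussion/Conclusions says that the trial "did show a lower overall score in the PICO-7 group vs the standard abdominal dressing group at the 6 week mark". That section reports no complication and does not mention the early removal of the dressing.

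**The concern.** Many readers see only the abstract and the conclusion. From the abstract they learn of one PICO complication, while the table has two. From the Discussion/Conclusions they learn which way the scar scores pointed, but nothing about complications. If the authors think a direction on benefit is worth stating at this sample size, the small numbers cannot be the reason for silence on the secondary objective.

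The omitted event is not remote from the trial's subject. The Background lists pain among the consequences of pathological scars, and pain is one of the six patient items of the POSAS. The documents give no reason for naming one itemised event and leaving out the other. The abstract's disclosure that the manufacturer part-funded the study makes even-handed reporting more important.

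The infection statement rests on no events in two very small groups, and a reader without the denominators may take it as reassurance.

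**Working it through.** **Inputs** (Protocol: the complications table in Secondary Outcomes; the enrolled number from Statistical Analysis; the analysed number from Patient demographics)

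| | Standard (N = 5) | PICO (N = 10) |
|---|---|---|
| None | 4 (80%) | 8 (80%) |
| Adhesive rash | 0 | 1 (10%) |
| Neuropathic pain | 0 | 1 (10%) |
| Infection | 0 | 0 |
| Dehiscence | 0 | 0 |

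Enrolled: 24. Included for analysis: 15.

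**Step 1. Does each column close?**
- PICO: 8 + 1 + 1 = 10. The percentages 80, 10 and 10 reproduce, so the two events fell in two different patients.
- Standard: 4 + 0 = 4, against N = 5. One patient is unplaced.

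**Step 2. Abstract against table, PICO arm.** The abstract names 1 event and the table 2, so half of the itemised events are missing from the abstract.

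**Step 3. Precision.** Exact (Clopper-Pearson) 95% limits for x events in n patients: the lower limit is the 0.025 quantile of Beta(x, n − x + 1), and the upper limit is the 0.975 quantile of Beta(x + 1, n − x). For x = 0 the upper limit is 1 − 0.025^(1/n).

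| Quantity | Estimate | Exact 95% CI |
|---|---|---|
| PICO, both events, 2/10 | 20% | 2.5% to 55.6% |
| PICO, rash only, 1/10 | 10% | 0.3% to 44.5% |
| PICO, infection, 0/10 | 0% | 0% to 30.8% |
| Standard, infection, 0/5 | 0% | 0% to 52.2% |

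**Step 4. Between-arm comparison under each reading of the fifth standard-dressing patient.**

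| Standard arm | Rate (exact 95% CI) | PICO minus standard | Fisher two-sided p |
|---|---|---|---|
| 0/5 (no complication) | 0% (0% to 52.2%) | 20 points | 0.52 |
| 0/4 (not assessed) | 0% (0% to 60.2%) | 20 points | 1.00 |
| 1/5 (a complication not itemised) | 20% (0.5% to 71.6%) | 0 points | 1.00 |

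The None row reads 80% in both arms. Taken at face value, that agrees with the last line.

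**Step 5. Coverage.** The table describes 5 + 10 = 15 patients. 15/24 = 62.5%, so 24 − 15 = 9 enrolled patients (37.5%) are absent from it.

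**Step 6. Readmissions.** The complications table has no readmission row, and no readmission count appears in the text or tables supplied.

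**The case against.** The strongest reply is that this is loose drafting and not a favourable slant. The abstract volunteers that the rash led to early removal, a detail the table lacks. It also says that PICO scores were higher, hence worse, at 2 weeks, while Table 2 shows medians of 19.0 for PICO and 33.0 for standard dressing. That error runs against the device. The abstract's Conclusion disclaims any evaluation of the dressings and cites potential benefit only as a reason for further research. The statement on infection numbers is literally true (0 and 0). The full table is in the same document, and one event in 10 patients supports no safety inference.

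Most of this stands, and it limits the point. Intent is not at issue, and the abstract's Conclusion is not where the imbalance lies. The imbalance is in the Discussion/Conclusions, where a direction is given for scar scores and nothing for complications, even though that section concedes that nothing was statistically significant. None of the reply explains why one of two itemised events was left out.

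A reader might go further and infer that complications occurred only under PICO, or that the device carries more harm. The documents do not support either reading. The fifth standard-dressing patient is unplaced, so the excess could be zero. The table gives no cause, site, onset or duration for the neuropathic pain, and nothing attributes it to the device. Nor does the abstract state a rate of 1 in 10: it gives no complication denominator, and its only patient number is the 24 enrolled.

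**Conclusion.** The point holds as one of incomplete reporting. The abstract gives one of the two PICO complications in the study's own secondary-outcome table (2/10, 20%, exact 95% CI 2.5% to 55.6%). The Discussion/Conclusions leave the only secondary objective unanswered while stating a direction in favour of PICO on scar scores.

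It does not hold as a harm signal. The PICO excess is 0 to 20 percentage points depending on one unplaced patient, with Fisher p from 0.52 to 1.00. The infection counts neither show nor exclude a difference, since rates up to 31% and 52% are compatible with them.

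This rests on two assumptions: the PICO column is right as printed, which its closing to 10 supports, and the nine enrolled patients outside the table contribute no known events. The documents do not say whether they do. No estimate or analysis changes. The correction should be made because it concerns the only secondary objective and costs little.

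**What to change.** 1. Check the record of the fifth standard-dressing patient, place that patient in the table, and remove the drafting query. Do this before writing any between-arm wording.
2. In the abstract, report both itemised PICO events with denominators (one adhesive rash with early removal and one neuropathic pain, 2/10), beside the resolved standard-arm count. Give infections as 0/10 and 0/5 with exact 95% upper limits of 31% and 52%, in place of the bare statement that the numbers did not differ. State that the table covers 15 of the 24 enrolled patients.
3. Support the readmission statement with counts by arm, or remove it.
4. In Discussion/Conclusions, add the secondary-objective result and say that the data can neither show nor exclude a difference in complications. Claim neither a harm signal nor device causation.

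The cost is one record check, a source for the readmission counts if that statement is kept, and a few sentences. The safety statement becomes slightly less favourable to the device.
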